6.8 Recommended concomitant therapies and permitted drugs

The use of anticomitial drugs will be allowed, as prophylaxis, if patients are already on antiepileptic therapy, as well as the continuation of steroid therapy if already in place. The following drugs and / or supportive therapies can be used, if clinically indicated:

- steroids;
- antiemetics;
- mannitol i.v .;
- anticomitial drugs.

6.9 Concomitant Therapies Prohibited

During the entire duration of the treatment it will not be allowed to use:

- antineoplastic drugs;
- other experimental drugs.

7. EXIT FROM THE STUDY AND SUSPENSION OF THE TREATMENT

7.1 Exit from the study

Should one of the following conditions occur, the patient should be considered off-study and will not be included in the study's end point analysis:

- a. refusal of the patient to continue the treatment (withdrawal of informed consent);
- b. violation of the inclusion / exclusion criteria.

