4. OBJECTIVES

4.1 Primary objective

The study proposes the evaluation of the side effects of the proposed experimental radiotherapy treatment and the acceptability of the risk / benefit ratio.

Acute / subacute toxicity will be analysed with recording of adverse events (related or unrelated) reported during the entire treatment and within 3 months of its end.

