7.2 Suspension of treatment

Treatment must be permanently suspended if one or more of the following situations occur:

- grade > 3 neurological and non-neurological toxicity;
- grade ≤ 2 neurological toxicity unresponsive to supportive care;
- disease progression during treatment;
- second medical opinion, for safety reasons;
- refusal of the patient to continue the treatment;
- need to start antineoplastic therapy.

Permanent discontinuation of treatment, in case of disease progression or unacceptable toxicity, will be considered as a therapy failure, therefore patients will be included in the study's end-point analysis.

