9. OUTCOMES EVALUATION PLAN

The response to radiotherapy treatment will be evaluated according to the RANO criteria (Technical Annex) with morphological and functional (multiparametric) brain MRI performed at 1 month after the end of radiotherapy and then after 3 months.

The toxicity assessment will be made with reference to the International Common Toxicity Criteria for Adverse Event (CTCAE) - version 4.0 (The complete document is available on the website of the National Institute of Health

The response to radiotherapy treatment will be evaluated according to the RANO criteria (Annex) with morphological and functional (multiparametric) brain MRI performed at 1 month after the end of radiotherapy and after 3 months.

The toxicity assessment will be made with reference to the International Common Toxicity Criteria for Adverse Event (CTCAE) - version 4.0 (The complete document is available on the National Institute of Health (NIH) website at the following address: <http://ctep.cancer.gov/reporting/ctc.html>), excluding neurological adverse events of grade ≤ 2 that responded adequately to supportive care.

Safety and tolerability will be defined for:

- type, frequency, severity and relationship of adverse events to treatment;
- number of subjects who prematurely discontinued treatment due to any adverse event;
- frequency of clinically significant changes and / or laboratory tests.

All patients who have started radiation treatment will be considered for analysis, until the completion of the study (i.e. until the final visit at the end of the entire program for patients who complete the treatment) or until the scheduled follow-up visit in case of premature suspension of the study. Patients will be instructed by the Investigator on the need to report any adverse events that may occur during the study.

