12.2 Analysis plan

By virtue of the exploratory nature of the study and the limited number of subjects, the data will be presented mainly through tables and lists. Confidence intervals for percentages will be calculated following the Clopper-Pearson method to properly take into account the limited number of subjects. OS and PFS will be graphed using the Kaplan-Meier method and briefly described in percentile terms. The analyses will be conducted with R, SAS System, or SPSS software on the basis of availability at the time of the analyzes and in the versions in use in that period

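### Section 7.1 removes treated patients from the end-point analysis while section 9 analyses everyone who started radiation, and nothing says which rule governs the primary toxicity result

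*Combined protocol and SAP*

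**What the plan says.** Section 4.1 makes toxicity the primary objective, assessed through "recording of adverse events (related or unrelated) reported during the entire treatment and within 3 months of its end".

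Section 7.1 lists two conditions under which "the patient should be considered off-study and will not be included in the study's end point analysis". Trigger (a) is "refusal of the patient to continue the treatment (withdrawal of informed consent", where the bracket is the protocol's own gloss. Trigger (b) is "violation of the inclusion / exclusion criteria". Neither is limited to events before the first session.

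Section 9 sets out the safety and tolerability measures, among them the "number of subjects who prematurely discontinued treatment due to any adverse event". The next paragraph says: "All patients who have started radiation treatment will be considered for analysis".

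Section 7.2 lists refusal among the reasons for permanent suspension. The cases it expressly keeps are progression and "unacceptable toxicity, will be considered as a therapy failure, therefore patients will be included in the study's end-point analysis".

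Section 12.2 says "Confidence intervals for percentages will be calculated following the Clopper-Pearson method", but gives no denominator, analysis set or confidence level.

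**The concern.** Two kinds of patient fall under both rules: one who starts the five sessions and then refuses to go on, and one whose eligibility breach comes to light after irradiation. Section 7.1 takes both out; section 9 keeps both in.

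The first case matters more for a safety study. Someone who declines further sessions because of an adverse event belongs in section 9's count of adverse-event discontinuations, yet trigger (a) can remove that person from the analysis altogether. If refusals of this kind occur and are not classed as unacceptable toxicity, following section 7.1 would probably understate toxicity. For eligibility breaches the direction of any distortion cannot be predicted.

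With 12 patients and results shown mainly as tables and lists, the choice of patients largely determines the result. Leaving that choice open also allows it to be made after outcomes are known.

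**Working it through.** **Comparing the rules**

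| Treated patient | 7.1 | 7.2 | 9 |
|---|---|---|---|
| Stops for progression or unacceptable toxicity | not listed | kept | kept |
| Refuses further sessions, not classed as unacceptable toxicity | removed | suspended; not named among those kept | kept |
| Withdraws consent | removed | not addressed separately | kept |
| Eligibility breach found after irradiation | removed | not addressed | kept |

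The last three rows conflict between 7.1 and 9. Section 7.2 settles none of them. It might cover a refusal prompted by an adverse event, but only if the event counts as unacceptable toxicity, a term used in 5.1 and 7.2 without a formal definition.

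Related wording also needs attention. The study-exit cases in the 6.7 table (progression, and need for antineoplastic therapy) share no item with the exit list in 7.1; the 6.7 table treats refusal as suspension only. Section 13.1 stops a withdrawn patient's data from contributing from that moment on and is unclear about data already collected. Section 13.3 continues monitoring after early termination of treatment, but this can end at exit from follow-up. The wording of 13.1 and 13.3 should be aligned, but neither is a direct conflict.

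**Size of the effect (illustration)**

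The plan has no toxicity figure to reproduce; its 12 is a feasibility number (section 12.1). Inputs:
- From the plan: n = 12 and the Clopper-Pearson method (12.2).
- Assumed: all 12 treated, one yes/no event per patient (for example, stopping treatment because of an adverse event), the event counts, and a two-sided 95% level.

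Exact limits for x events in n patients are the α/2 quantile of Beta(x, n − x + 1) and the 1 − α/2 quantile of Beta(x + 1, n − x). The lower limit is 0 when x = 0.

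Dropping one event patient changes the rate by (x − 1)/(n − 1) − x/n = −(n − x)/[n(n − 1)], which is −(12 − x)/132 here. Dropping one event-free patient changes it by x/[n(n − 1)] = x/132.

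| All treated (section 9) | Dropped under 7.1 | Result | Change, points |
|---|---|---|---|
| 1/12 = 8.3% (0.2–38.5) | 1 with event | 0/11 = 0% (0–28.5) | −8.3 |
| 1/12 | 1 without | 1/11 = 9.1% (0.2–41.3) | +0.8 |
| 2/12 = 16.7% (2.1–48.4) | 1 with event | 1/11 = 9.1% (0.2–41.3) | −7.6 |
| 2/12 | 2 with event | 0/10 = 0% (0–30.8) | −16.7 |
| 2/12 | 1 without | 2/11 = 18.2% (2.3–51.8) | +1.5 |
| 2/12 | 2 without | 2/10 = 20.0% (2.5–55.6) | +3.3 |
| 3/12 = 25.0% (5.5–57.2) | 1 with event | 2/11 = 18.2% (2.3–51.8) | −6.8 |
| 3/12 | 1 without | 3/11 = 27.3% (6.0–61.0) | +2.3 |

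At an assumed 90% level the changes in the rate are identical and only the limits move; for example, 2/12 then has limits 3.0–43.8 and 1/11 has 0.5–36.4.

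**The case against.** The best defence reads trigger (a) by its gloss, as withdrawal of consent only. The 6.7 table makes refusal a suspension and not an exit. Section 7.2 again lists it under suspension, and 7.3 separates consent withdrawal from other discontinuations, giving the latter a follow-up visit. On this reading a patient who only declines further sessions stays in. That is a fair reading and would remove much of the most worrying mechanism. It still drops treated patients who withdraw consent, and it does nothing about trigger (b).

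A second defence is that section 9's sentence, placed right after the safety measures, defines the safety set, leaving 7.1 for other endpoints. The placement does suggest this, but the text does not say it. Section 7.1 speaks of the study's endpoint analysis without restriction, and toxicity is the primary endpoint.

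Trigger (b) may have been aimed at registered patients found ineligible before treatment, since eligibility is assessed before a number is assigned (3.3). As written, it has no such limit.

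Some points of scale stand. Treatment lasts only five daily sessions, so the window for refusing to continue is short. Adverse events are recorded in the CRF in any case (sections 10 and 10.2). The interim reports are less exposed, because 12.1 bases them on cases already treated. The study is exploratory, with no hypothesis test or final threshold. These limit how often the conflict will matter and what it can alter; they do not resolve it.

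**Conclusion.** The concern holds. Applied as written, section 7.1 can remove irradiated patients from the primary toxicity analysis of a 12-patient safety study, against section 9, and no section decides between them. This is a conflict in the stated rules and must be fixed.

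If 12 are treated and 1 to 3 have the event, one dropped event patient lowers the reported rate by 6.8 to 8.3 points and can erase the only event seen. One dropped event-free patient raises it by 0.8 to 2.3 points. These figures rest on assumed counts and a binary event; the plan does not allow the number of such patients to be estimated. Confidence is high that the rules conflict. That toxicity would be understated is only probable, and only for refusals that follow poor tolerance without being classed as unacceptable toxicity.

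**What to change.** - In 7.1, remove the exclusion of irradiated patients as far as toxicity is concerned.
- In 12.2, name all patients who started radiation as the primary toxicity set, and use the same set for the interim reports.
- Distinguish refusal of further sessions from withdrawal of consent. For withdrawal, use data up to that date as far as consent allows, and count and list each case.
- Keep treated eligibility violators in the set and flag them in the listings.
- Define unacceptable toxicity, as used in 5.1 and 7.2, for the purpose of classifying patients in the analysis, or stop using it to decide who is analysed.
- Reconcile the exit lists in 6.7 and 7.1, and align 13.1 and 13.3 with the result.

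The cost is protocol wording, with no added patients or visits. The consent text should be checked for what it permits with data collected before withdrawal. The reported toxicity rate may be less favourable than under 7.1.

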7.2 Suspension of treatment

Treatment must be permanently suspended if one or more of the following situations occur:

- grade > 3 neurological and non-neurological toxicity;
- grade ≤ 2 neurological toxicity unresponsive to supportive care;
- disease progression during treatment;
- second medical opinion, for safety reasons;
- refusal of the patient to continue the treatment;
- need to start antineoplastic therapy.

Permanent discontinuation of treatment, in case of disease progression or unacceptable toxicity, will be considered as a therapy failure, therefore patients will be included in the study's end-point analysis.

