6. TREATMENT PLAN

6.1 Radiotherapy treatment

The treatment envisaged by the protocol involves the planning and execution of a hypofractionated radiotherapy (RT) treatment, administered in 5 daily sessions, with modulated intensity technique and inhomogeneous distribution of the dose guided by diffusion images obtained with magnetic resonance imaging (MRI).

The radiotherapy treatment must begin within 7 days from the date of execution of the centering MRI which will include both the classic morphological sequences with administration of contrast medium and functional. In this regard, for more details see the Technical Annex.

In selected cases and according to clinical judgment, it will be possible to request a review of the anatomic-pathological and radiological findings.

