6.6 Dose prescription

6.6.1 Target dose

The prescription dose provides for a minimum dose of 30 Gy (6 Gy per session) for the areas with the highest ADC, with a gradual increase in the dose for the areas with the lowest ADC. The maximum hypothesized dose is 50 Gy, with a dose of 10 Gy per session at no more than 1cc of irradiated brain tissue. For more details see the Technical Annex.

The treatment plan, however, will be developed according to the following order of priority:

1. Compliance with dose limits for primary OAR.
2. PTV coverage.
3. Compliance with dose limits for secondary OARs.

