6.7 Changes or suspension of treatment

During the treatment program, neurological toxicities will be evaluated according to criteria of the National Cancer Institute Common Toxicity Criteria for Adverse Events (NCI CTCAE), version 4.0. The patient will be monitored for the appearance of adverse events for the entire duration of the study, including the follow-up period.

Events	Actions
a) Neurological toxicity \leq grade 2 responsive to supportive care b) Grade \leq 3 non-neurological toxicity	The RadioTherapy treatment continue
c) grade $>$ 3 neurological and non-neurological toxicity; d) grade \leq 2 neurological toxicity unresponsive to supportive care; e) disease progression during treatment; f) second medical opinion, for safety reasons; g) refusal of the patient to continue the treatment; h) need to start antineoplastic therapy.	The presence of at least one of the events determines the definitive suspension of the treatment. It also involves leaving the study in cases (e) and (h)

In case of grade \leq 2 neurological toxicity with response to adequate supportive therapy (steroids, mannitol, anticomitials) the radiotherapy treatment will continue.

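### Sections 6.7 and 7.2 state no action for grade 3 neurological toxicity during the five-session course, although they require a permanent stop for unresponsive grade 1-2 events

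*Combined protocol and SAP*

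**What the plan says.** Section 6.7 has a two-row table of events and actions.

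- **Continue.** Item (a) covers neurological toxicity at or below "grade 2 responsive to supportive care". Item (b) covers non-neurological toxicity up to and including grade 3. The sentence under the table repeats the condition in (a).
- **Definitive suspension.** Item (c) is toxicity above grade 3 of either type. Item (d) is neurological toxicity of grade 2 or less that does not respond to care. The remaining items are progression, patient refusal, need for antineoplastic therapy, and "f) second medical opinion, for safety reasons". One item is enough: "The presence of at least one of the events determines the definitive suspension of the treatment".

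Section 7.2 repeats the suspension list as mandatory and permanent, including "grade > 3 neurological and non-neurological toxicity" and "grade ≤ 2 neurological toxicity unresponsive to supportive care".

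Toxicity is graded by CTCAE version 4.0, on a scale from 1 to 5 (section 10.1.1). The treatment is a "hypofractionated radiotherapy (RT) treatment, administered in 5 daily sessions" (section 6.1).

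**The concern.** A rule for stopping treatment should cover every grade and should not become more lenient as severity rises. This one appears to fail on both counts for neurological toxicity. The continue row uses different limits for the two types (grade 2 for neurological, grade 3 for non-neurological), while item (c) applies a single limit, above grade 3, to both. Grade 3 neurological toxicity falls between them.

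At stake are patient protection and consistent handling. Section 2 makes safety the primary objective because there is no clear evidence on toxicity in brain tissue that has already been irradiated, and section 6.6.2 says that there are no established dose limits for this kind of retreatment. With daily sessions there is little time to settle an ambiguity before the next fraction. Two investigators could read the same text and act in opposite ways on the same event.

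**Working it through.** **Step 1: set each grade against the rules.** The inputs are items (a) to (d) of section 6.7, the list in 7.2, and the grade range of 1 to 5 in 10.1.1.

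| Type | Grade | Responds to care? | Action as written |
|---|---|---|---|
| Neurological | 1-2 | yes | continue (a) |
| Neurological | 1-2 | no | stop (d) |
| Neurological | 3 | yes | none stated |
| Neurological | 3 | no | none stated |
| Neurological | 4-5 | either | stop (c) |
| Non-neurological | 1-3 | either | continue (b) |
| Non-neurological | 4-5 | either | stop (c) |

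Only the two grade 3 neurological rows have no action. No other section assigns one. Along the unresponsive neurological rows, the mandatory list reads: grades 1-2 stop, grade 3 no requirement, grades 4-5 stop.

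**Step 2: could the strict inequality be a misprint?** It stands in both 6.7 and 7.2. If item (c) were read as grade 3 or above for both types, it would stop treatment for non-neurological grade 3, which item (b) says continues. That reading would put the section in conflict with itself. If instead (d) were meant as grade 2 or above, a grade 3 event that responds would still have no rule.

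**Step 3: dose still to come when the gap is reached.** The inputs are five sessions (6.1) and two statements in 6.6.1: "The prescription dose provides for a minimum dose of 30 Gy (6 Gy per session) for the areas with the highest ADC" and "The maximum hypothesized dose is 50 Gy, with a dose of 10 Gy per session at no more than 1cc of irradiated brain tissue". The plan's own figures agree: 30/5 = 6 Gy and 50/5 = 10 Gy per session. After session k, the sessions left are 5 − k, the minimum target dose left is 6 × (5 − k), and the maximum (in at most 1 cc) is 10 × (5 − k).

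| After session | Sessions left | Minimum left in target | Maximum left, in ≤ 1 cc | Share of course |
|---|---|---|---|---|
| 1 | 4 | 24 Gy | 40 Gy | 4/5 = 80% |
| 2 | 3 | 18 Gy | 30 Gy | 3/5 = 60% |
| 3 | 2 | 12 Gy | 20 Gy | 2/5 = 40% |
| 4 | 1 | 6 Gy | 10 Gy | 1/5 = 20% |

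These figures show how much treatment the missing decision governs. They do not measure harm.

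**Step 4: does the gap reach the primary endpoint?** Section 9 leaves out only neurological events of grade 2 or less that responded to care, so a grade 3 event is counted whatever is done about it. Section 9 also counts patients who stop early because of any adverse event, so a discretionary stop for such an event is counted too.

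**Step 5: repeat step 1 with the neurological limit at grade 3 or above and the non-neurological limit unchanged.** Neurological grade 1-2 responsive continues, grade 1-2 unresponsive stops, and grade 3-5 stops. Non-neurological grade 1-3 continues and grade 4-5 stops. Every row now has exactly one action, and the rule no longer softens as severity rises.

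**The case against.** The strongest reply is that silence is not permission. Section 6.7 allows continuation for neurological toxicity only at grade 2 or less with response, and says so twice. Grade 3 lies outside that set, so a careful investigator would stop. This is a fair reading, and probably the intended one. But 7.2 is the operative list of when treatment must stop, and it omits grade 3 neurological toxicity. The intent therefore has to be inferred.

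The second reply is that item (f) covers the case. A reader might take it to need a second doctor's opinion that nobody is obliged to seek. The text does not settle that. The document reads as a literal translation, and the item may simply mean the treating physician's judgment; section 6.1 speaks of clinical judgment in another context. On that reading the physician can stop treatment directly, which narrows the gap. It does not close it, because the item carries no grade or criterion, while milder unresponsive events carry a mandatory stop.

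Third, other provisions limit the consequences. Section 10.1.3 requires the action taken for each event to be recorded, and section 5.2 allows the study to end early if risk and benefit become unacceptable. Both stand, but neither says what to do about a grade 3 neurological event between sessions.

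Finally, the course is short, so few patients may reach the gap. The documents give no rate of such events, so how often it would arise cannot be stated.

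**Conclusion.** The point holds as an omission. Sections 6.7 and 7.2 give no action for grade 3 neurological toxicity, and the mandatory stop list, read literally, is stricter for unresponsive grade 1-2 events than for unresponsive grade 3 events. The remaining treatment left to discretion ranges from one session (at least 6 Gy to the target) to four (at least 24 Gy). The 10 Gy per session maximum applies to at most 1 cc. The conclusion rests on the inequalities as printed in both sections, which step 2 supports.

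Two stronger conclusions are tempting and should not be drawn. A reader might infer that the protocol authorises further sessions after an unresponsive grade 3 neurological event. It does not: no text permits continuing, and the continue row points the other way. A reader might also infer that the toxicity results are compromised. They are not, because such events are recorded and counted under section 9 either way.

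The correction should be made because toxicity is the primary objective and the change is very cheap. It alters no sample size and no analysis.

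**What to change.** In section 6.7(c) and the first bullet of 7.2, replace the current criterion with: *neurological toxicity grade ≥ 3, or non-neurological toxicity grade > 3*. This matches the limits already in the continue row. Items (a), (b) and (d) and the sentence under the table stay as they are.

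If the sponsor does not want every grade 3 neurological event to end treatment, the least that should be done is to make grade 3 neurological toxicity unresponsive to supportive care a mandatory stop. That removes the reversal between grades, but leaves grade 3 that responds without a stated action.

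The cost is a wording change in two places, with no added patients, visits or procedures. The drawback of the full fix is that a patient whose grade 3 neurological event responds to care would stop the course early and could be counted as a therapy failure under 7.2. Whether that is acceptable is a clinical decision for the sponsor.
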